The primary hypothesis is that PASC reduce complications up to 30 days after surgery. Secondary hypotheses are that PASC reduce readmissions to hospital, length of hospital stay, and mortality up to 30 days after surgery.

Complications are in this trial observations of the surgical complications registered in patients' medical records and coded according to the International Classification of Diseases – 10th version (ICD-10) by surgeons or ward doctors. One or more complications per hospital stay per patient will be given the values zero or one, as the main outcome variable. Similarly, secondary outcomes. i.e. mortality, will be given zero or one (for events).

Statistical power

In protocol version 1.0, the sample size was calculated to be 4200 cases across the clusters. Based on data from a pilot of PASC feasibility (Harris et al, 2023), an update was required. The sample size analysis was updated in protocol 2.0 (30th June 2021):

The pooled overall proportion of surgery-related complications (i.e. infections, bleedings, cardiac or lung related) has previously been estimated to be 15% and is the primary outcome for the present analysis (Storesund et al, 2020). We propose that the inclusion of PASC will lower this proportion by at least 5% (corresponding to a 33.3% relative risk reduction). Using the stepped wedge power analyses command in Stata (*steppedwedge* command), we calculated that the lowest number of individuals required to detect the 5% reduction is 5320. The calculation was carried out using a non-standard stepped wedge design (see diagram below): 7 wards x 20 months x 38 patients (on average). We further assumed that the intra-cluster correlation (ICC) was 0.05 and that the type I error and type II error were 0.05 and 0.20, respectively.

Statistical analyses

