Harris et al. Development and validation of patients' surgical safety checklist. BMC Health Services Research. 2022; 22:259.

Kline RB. Principles and Practice of Structural Equation Modeling. Third edition. The Guilford Press. New York, USA, 2011.

Weiner et al. Psychometric assessment of three newly developed implementation outcome measures. Implementation Science. 2017; 12:108.

Statistical analysis plan part d) for the PASC Health Economic Impact (PASC-HEI)

Health economic evaluations of patient safety interventions in healthcare are limited, though previously we have evaluated the cost-effectiveness of the World Health Organization's Surgical Safety Checklist (Healey et al. 2022). It is vital to evaluate the impact of new patient safety interventions on costs and benefits for patients and society. Hence in the PASC trial we aim to investigate the health economic impact of the Patient Safety Checklist (PASC) in the PASC Stepped Wedge Cluster Randomized Controlled Trial ([name], 2017).

The main hypothesis is that the PASC is cost-effective for both patients and society. Primary outcome is costs associated with implementation of the PASC, where length of hospital stay is a major component for the overall treatment cost (Healey et al, 2022).

Statistical power of the PASC trial on PASC-HEI

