The statistical power of the PASC trial is based on sample size calculations referred to in the protocol and in the Statistical Analysis Plan for the trial, where 2660 in each arm with a total of 5320 cases would be required to detect a 5% reduction of events. The clinical data from the trial and health economic data such as the costs of PASC implementation and the cost of length of stays in hospitals, would be regarded to be adequate also for the cost-benefit analysis (Healey et al, 2022). The implementation variables include cost for time spent on implementation meetings with managers and staff, staff salaries, printing of checklists, mail costs, and digital distribution of the PASC checklist costs. Further, the variables also include costs for the patients due to actions taken after using the PASC checklist, like going to their general practitioner, dentist, nutritional diets (risks of malnutrition), and other relevant actions caused by the checklist intervention. The patient data is based on the clinical trial data and a patient survey (PASC health economic impact survey – “PASC HEI”) forwarded to a random sample drawn from within the trial. An adequate sample was calculated to 50 respondents from each cluster,

in each arm, 700 in all with a response rate at 50% (see sample calculations for the HLQ and EQ-5D-3L).

Statistical analysis plan of the PASC-Health Economic Impact data

Descriptive analysis with frequencies, percentages, mean scores, standard deviations will be applied for the patient characteristics, both for the PASC-HEI survey and for the economic evaluation of the trial. To investigate the PASC intervention impact on the health economic survey, a chi-squared test, or an independent samples t-test (ANOVA) will be used as appropriate to test for any differences between the trial arms. If there are significant variation in patients' characteristics between the two arms, a linear regression model (General Linear Model) will be applied to adjust for it and to compare effects. Analysis will be performed in SPSS 29.0 (IBM Corp, Armonk, NY) and a two-sided P value at 0.05 will be considered statistically significant.

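### Part d counts patient costs only as consequences of the checklist yet tests the survey between arms; as worded, the test can only show higher cost under PASC

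*SAP*

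**What the plan says.** The hypothesis at the start of SAP part d (PASC-HEI) reads: "The main hypothesis is that the PASC is cost-effective for both patients and society".

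The section on statistical power for PASC-HEI lists the cost variables. It begins with implementation costs (meetings, salaries, printing, mail, digital distribution) and then adds the patient costs: "costs for the patients due to actions taken after using the PASC checklist, like going to their general practitioner, dentist", nutritional diets, and "other relevant actions caused by the checklist intervention". Patient data come from the clinical trial data and from a survey "forwarded to a random sample drawn from within the trial". The survey sample is 50 respondents from each cluster, "in each arm, 700 in all with a response rate at 50" per cent.

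The analysis section for the PASC-HEI data states that, for the survey, a chi-squared test or independent-samples t-test "will be used as appropriate to test for any differences between the trial arms", and that "a two-sided P value at 0.05 will be considered statistically significant". If patient characteristics differ between arms, a linear model adjusts for them.

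The overview of work packages near the start of the SAP words the secondary outcome of item d differently. There it is patient costs connected with the patients' surgical treatment, with no reference to the checklist.

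**The concern.** Both phrases that define the patient costs make use of the checklist part of the definition. A control-period patient has not used it and, on a literal reading, scores zero on every such item. Patients awaiting surgery may nevertheless see a GP or dentist, or change their diet, without any checklist. Part d names no item that counts those costs in the control arm.

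Three consequences follow for a between-arm test of these items:

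- The difference can only be zero or positive. A reduction in visits under PASC could not be seen.
- The figure is a gross cost resting on each patient's own attribution. The hypothesis about cost-effectiveness for patients needs an incremental cost.
- Adjustment for patient characteristics does not help, because the control value is fixed by definition and not by case mix.

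At stake is the conclusion on patient costs, which the overview names as a secondary outcome of this part.

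**Working it through.** **Inputs from the SAP.** 7 wards (power section of part a); 50 patients per cluster per arm and 50% response (part d); 35% as a possible response rate (HLQ sample-size section, to which part d refers); two-sided alpha 0.05 (part d).

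**The plan's own figures.** 7 × 50 × 2 = 700, as stated, so 350 per arm. The HLQ calculation behind it (difference 0.30, SD 0.66, power 90%) gives 2 × (1.960 + 1.282)² × 0.66² / 0.30² ≈ 102 per arm, against 103 stated. No figure is disputed; the problem is the definition.

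**Respondents per arm.** 350 × 0.50 = 175; 350 × 0.35 = 122.5, taken as 122.

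**How few reports make the test significant.** With *m* respondents per arm, *k* PASC patients reporting an action and control fixed at 0, the chi-squared statistic without continuity correction is 2mk / (2m − k).

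- m = 175, k = 4: 350 × 4 / 346 = 4.05, p = 0.044. Four of 175 is 2.3%.
- m = 122, k = 4: 244 × 4 / 240 = 4.07, p = 0.044. Four of 122 is 3.3%.
- k = 3 at m = 175: 350 × 3 / 347 = 3.03, below the 3.84 needed.

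Fisher's exact test would need six reports (p = 0.030 at m = 175, 0.029 at m = 122).

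**Rejection when PASC changes nothing.** Suppose both arms truly act at the same rate *r* but only the PASC arm's actions are counted. The chi-squared test then rejects with probability P(X ≥ 4), X ~ Binomial(m, r). The SAP gives no action rates, so *r* is assumed.

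| r | m = 175 | m = 122 |
|---|---|---|
| 2% | 0.46 | 0.23 |
| 5% | 0.98 | 0.86 |
| 10% | 1.00 | 0.999 |

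The t-test was simulated with 4,000 runs per row and an assumed gamma cost (shape 1) for each patient who acts:

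| r | m | Control fixed at 0 | Same items in both arms |
|---|---|---|---|
| 5% | 175 | 0.74 | 0.042 |
| 10% | 175 | 0.99 | 0.043 |
| 20% | 175 | 1.00 | 0.050 |
| 5% | 122 | 0.44 | 0.039 |
| 10% | 122 | 0.93 | 0.042 |
| 20% | 122 | 1.00 | 0.043 |

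Counting the same items in both arms restores a rejection rate at or just below the nominal 5%.

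**Size of the misstatement.** As an illustration with assumed rates, let 30% of control and 40% of PASC patients have one contact at equal unit cost. The true increment is 0.40 − 0.30 = 0.10. If PASC patients attribute a share *a* of their contacts to the checklist, the recorded increment is 0.40a and its ratio to the truth is 4a. That is 1 at a = 0.25, 2 at a = 0.5 and 4 at a = 1, and below 1 when a is under 0.25. The ratio therefore depends on attribution, which the SAP cannot inform.

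**The case against.** The strongest reply is that the sentence belongs to a list of what it costs to deliver PASC. Printing and meetings are also zero in control, and entering checklist-induced costs with zero in the comparator is ordinary incremental costing. That is right as far as it goes, but it requires that the induced costs be truly incremental, and it gives no reason to test them between arms.

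A second reply is that the analysis section names no variable for the survey test, and the questionnaire is not shown. Surveying controls makes more sense if some items can be answered in both arms, and the overview's wording points the same way. This stands as a limit: *as worded* is the most that can be said. But part d itemises no other patient cost, so the text an analyst would follow leads to the asymmetric comparison.

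A third reply is that overstated patient costs work against the trial's hypothesis, so a favourable result would survive. This holds only if attribution is high enough. In the illustration above, attribution below 25% understates the cost.

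A reader might go further and infer that part d's hypothesis cannot be answered at all, or that any societal claim must be dropped. The SAP does not support that. The cost-effectiveness analysis uses total cost per admission and 30-day complication-free admissions. Length of stay and complications are measured in both arms and can move either way. A reader might also infer that the survey test is certain to be significant; at a 2% action rate the chi-squared test rejects with probability only 0.23 to 0.46.

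**Conclusion.** The point holds for the survey-based comparison of patient costs and no further. Followed literally, part d compares a checklist-attributed cost with a structural zero. Such a test can only point towards higher cost under PASC, and four reports in one arm are enough for significance at the planned sample. The recorded amount is gross, and the SAP gives no basis for saying how far it departs from the incremental cost. The overview and part d also describe the patient-cost outcome differently and must be reconciled.

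The rejection probabilities rest on assumed action rates, an assumed cost distribution for the t-test, and response rates of 35% to 50%. The direction of the test follows from the definition alone. If the questionnaire already asks neutral questions in both arms, only the SAP's wording is at fault.

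**What to change.** Define the compared patient-cost items identically in both arms: all GP, dentist, diet and similar costs in the same fixed window around surgery, whatever the reason. Estimate the patient cost of PASC as the between-arm difference in those totals. Report checklist-attributed costs descriptively, in the intervention arm only. Align the overview and part d on this definition.

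If the survey wording is already fixed and asks only about attributed actions, do not test these items between arms. Label them as gross intervention-arm cost and limit the conclusion on patient costs accordingly.

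The cost is a change of SAP wording, plus one reworded block of questions if any survey is still to be sent. The downside is that all-cause costs are noisier than attributed ones, so the estimate will be less precise.

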The main goals of the study are to investigate the impact of a patient safety checklist on patients having surgery within different surgical specialties, in three Norwegian hospitals (rural, central, and university hospital). The study has several work packages and hypothesis: a) The PASC checklist is hypothesized to have effect on surgical patients’ complications, reoperations, readmissions, length of stay and mortality. Of these variables, complications are the primary outcome. Further, patients’ experiences are hypothesized to be positively impacted by using PASC. Primary outcome for this part is the Patient Safety Checklist Experience Questionnaire. b) One part of the PASC checklist project include patients’ self-screening on their risk of malnutrition, prior to surgery. Main hypothesis is that the PASC have impact on nutritional outcomes. Nutritional complications are a primary outcome for this part of the study, and secondary outcome are comparison of patients and healthcare staffs’ risk assessments by comparing use of the Malnutrition Screening Tool. c) Investigate how implementation of the PASC checklist, a patient safety intervention, may be optimally used by the patients. Primary outcome is feasibility and compliance to using the checklist. Further, patients experiences are hypothesized to be positive towards the implementation. Primary outcome of this part is the PASC implementation survey. d) PASC is hypothesized to have an impact on cost-benefit of patients and the healthcare services. For this part of the study, the primary outcome is cost-effectiveness of the implementation across a-c. Secondary outcomes are the patient costs attributed associated with their surgical treatment. e) The PASC checklist is hypothesized to have impact on patients’ health literacy. Primary outcome is the nine dimensions of the Health Literacy Questionnaire. f) PASC is hypothesized to have impact on patients’ Quality of Life. Primary outcome is the EuroQual-5D-3L questionnaire.

Explanations of the statistical analysis techniques used for analyzing the data in the trial are detailed in the pages below.

Reference

Harris et al. Development and validation of patients’ surgical safety checklist. BMC Health Services Research. 2022; 22:259.

Statistical analysis plan a) for the PASC Stepped Wedge Cluster Randomized Controlled Trial

Hypothesis

[figure not shown]

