For the evaluation of implementation costs in combination with the clinical outcome data (i.e. complications and length of stay) the analysis builds on empirical data from the trial and our previous analysis methods published by Healey et al. (2022). In the cost-effectiveness analysis the mean difference in the absolute probability of the hospital admission is linked to a procedure being complication free, from control to intervention arms. We will investigate 30-days complication-free hospital admissions per 100 admissions. Ordinary least squares regression with a binary approach will be used to identify mean differences of the total costs per admission and the probability of hospital admissions without complications. A nonparametric approach will be used to estimate standard errors on mean cost effects with 95% confidence intervals.

We will estimate the cost impact of the PASC for a hospital bed-day equivalent and express the estimated cost difference as a "quality adjusted life year" (QALY). In Norway, the cost-effectiveness threshold is estimated by Woods et al (2016) to be between 43% and 93% of gross national income (GDP) per capita. We will present QALY equivalent effectiveness of the PASC as the lower, mid-point and upper-bound of this range (Healey et al, 2022).

Missing data on cost of hospital admissions and clinical covariates will be replaced with missing imputation (assumed missing at random) to reduce loss of power in the regression analysis (Azur et al, 2011). Missing data will be managed by creating 200 imputed datasets and the imputation model included all variables that to be included in adjusted regression model (Healey et al 2022). To test for sensitivity of the cost-effectiveness of the PASC implementation we use an upper and lower quartile excess bed-day cost from UK data to adjust for the Norwegian per diem costs (NHS, 2017).

The sample size calculation and the statistical analysis plan to be used on PASC-HEI was originally described in the 2.0 protocol, and updated 30th August 2024, by [name] [name], Department of Anaesthesia and Intensive Care, Haukeland University Hospital, Bergen, Norway; and Faculty of Health Sciences, Department of Nursing and Health Promotion, Acute and Critical Illness, Oslo Metropolitan University, Oslo, Norway.

References

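### Part d) asks whether PASC is cost-effective, but the only sampling uncertainty it plans is for cost, so the joint cost-effectiveness result has no specified interval

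*SAP*

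**What the plan says.** The SAP states the question of part d) in two places, and they differ. In the overview of work packages, item d), "the primary outcome is cost-effectiveness of the implementation across a-c". The opening of part d) gives the hypothesis, "The main hypothesis is that the PASC is cost-effective for both patients and society", and then says: "Primary outcome is costs associated with implementation of the PASC".

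The section on analysis of the health economic data describes the cost-effectiveness analysis. Ordinary least squares will be used to "identify mean differences of the total costs per admission and the probability of hospital admissions without complications". On sampling uncertainty it then says only: "A nonparametric approach will be used to estimate standard errors on mean cost effects with 95% confidence intervals".

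Two further steps vary the result. The cost difference is converted to a QALY equivalent using a threshold range of 43% to 93% of national income per capita: "We will present QALY equivalent effectiveness of the PASC as the lower, mid-point and upper-bound of this range". The sensitivity analysis uses "an upper and lower quartile excess bed-day cost from UK data". Missing data are handled with 200 imputed datasets. This section mentions neither clustering nor calendar time. Part a) has a random intercept for hospital and a calendar-month term.

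**The concern.** Cost-effectiveness is a statement about cost and effect together. An interval for the cost difference answers a narrower question, whether PASC changes cost. A checklist that leaves cost unchanged or slightly raises it can still be cost-effective if it prevents enough complications, and the cost interval does not show how certain that is.

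The plan produces both point estimates but no interval for any quantity that combines them: no net benefit, no interval for a cost-effectiveness ratio and no probability that PASC is cost-effective. The two estimates come from the same admissions. Part d) names length of stay as a major component of cost, so if complications lengthen stay, the two estimates are correlated. Two separate standard errors would not contain that correlation.

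At stake is the main hypothesis of one work package. The trial's primary complication outcome is not affected.

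**Working it through.** **Inputs from the SAP.** Complication risk 15% in the control period, lowered by 5 points to 10%; 7 wards × 20 months × 38 patients; ICC 0.05; type I error 0.05 and type II error 0.20 (part a, statistical power). 2660 per arm, 5320 in all (part d, statistical power).

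**The plan's own figure.** 7 × 20 × 38 = 5320 = 2 × 2660, which reproduces. The 80% power cannot be checked exactly because the rollout diagram is not shown. The SAP states no precision for cost, effect or cost-effectiveness.

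**Which planned steps carry sampling error?**

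| Step in part d) | Sampling error of cost | Sampling error of effect |
|---|---|---|
| Nonparametric SE and 95% interval | yes | no |
| QALY equivalent at three thresholds | none stated; the cost interval could be rescaled | no |
| Bed-day price quartiles | no (a price change) | no |

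**Size of the omitted effect-side error.** With independent patients and equal arms:

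- SE = √(0.15 × 0.85/2660 + 0.10 × 0.90/2660) = √(0.2175/2660) = 0.0090, or 0.9 points.
- 95% interval for a 5-point gain: 5 ± 1.96 × 0.904 = 3.2 to 6.8 points.
- For any fixed positive cost difference, the cost per additional complication-free admission then varies 6.77/3.23 = 2.1-fold from the effect alone.

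With ICC 0.05 the interval is wider. A standard stepped-wedge variance formula (Hussey and Hughes) at 38 patients per ward-month, under four assumed rollouts, gives an SE of 1.6 to 2.1 points. The 95% interval runs from about 1.9–8.1 points (best assumed rollout) to 0.9–9.1 points (worst). The corresponding fold ranges are 4.2 and 9.9.

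**Illustration of what a cost-only test can miss.** The SAP gives no standard deviation for cost or stay, no extra stay per complication and no value for a complication-free admission. Assume:

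- effect SE implied by 80% power: 0.05/(1.960 + 0.842) = 0.0178;
- length-of-stay SD 5 days, 5 extra days per complication, cost counted in bed-days, implementation cost ignored;
- correlation of stay with complication: 5 × √(0.125 × 0.875)/5 = 0.33.

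Cost only: saving = 0.05 × 5 = 0.25 bed-days; SE = 5 × 0.0178/√(0.125 × 0.875) = 0.27; z = 0.93; power = Φ(0.93 − 1.96) ≈ 15%.

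Net benefit, with L the value of a complication-free admission in bed-days: estimate = 0.25 + 0.05L; variance = 0.27² + (0.0178L)² + 2 × 0.33 × 0.27 × 0.0178L.

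| L | Net benefit | SE | Power |
|---|---|---|---|
| 5 | 0.50 | 0.31 | 36% |
| 10 | 0.75 | 0.37 | 53% |
| 20 | 1.25 | 0.51 | 68% |

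If the cost SE of 0.27 were used as the SE of net benefit, a nominal 95% interval would cover 2Φ(1.96 × 0.27/SE) − 1, which is about 91%, 85% and 70% at L = 5, 10 and 20 (SEs unrounded).

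Varying the SD over 4 to 8 days, the extra stay over 3 to 8 days and L over 5 to 20, cost-only power is 5% to 46% and net-benefit power 14% to 76%.

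**The case against.** The strongest reply is that part d) itself names implementation costs as its primary outcome, and a cost interval fits that outcome. This is a fair reading of one sentence. The sentence before it hypothesises cost-effectiveness, however, and the overview makes cost-effectiveness primary. The conflict is in the SAP and has to be settled there.

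A second reply is that the QALY equivalent is the cost difference rescaled, so its interval follows from the cost interval. That is arithmetically possible, but the plan does not say it will be done, and the result would contain no sampling error in the complication-free difference.

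A third is that the analysis builds on a published evaluation, which may specify the resampling. That source is not at hand. The SAP's own sentence is limited to cost.

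A reader might also infer more than the text supports:

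- *That no cost-effect pair is estimated, or that the effect has no standard error.* Both differences are estimated, and least squares on the binary outcome yields a standard error. The plan does not say it will be reported, and a default one ignores clustering. What is missing is joint uncertainty.
- *That the two results will be combined as if independent, to PASC's advantage.* Nothing plans this. An interval that is too narrow would in any case overstate certainty in either direction.
- *That significance of the cost difference will decide the hypothesis.* The two-sided 0.05 rule in part d) stands in the paragraph on the survey analysis. The SAP gives no decision rule for cost-effectiveness.

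**Conclusion.** The concern holds as a badly fixed analysis choice: the plan names a method for uncertainty and attaches it to cost, while its hypothesis concerns cost and effect jointly. No stated number is overturned.

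The firm part of the size rests on the plan's own rates. The omitted effect-side SE is 0.9 points with independent patients and larger with ICC 0.05, so it cannot be neglected. The range of 1.6 to 2.1 points depends on assumed rollouts.

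The power contrast (15% against 36% to 68%) is illustrative only. It depends on assumed stay, correlation and value per complication-free admission, and it sets implementation cost to zero although part d) itemises that cost. A positive implementation cost would reduce the saving and lower both powers. The change is worth making before the analysis.

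**What to change.** State one primary outcome for part d) and use it in both the overview and part d).

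Replace the cost-only standard error with a paired bootstrap:

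- In each replicate, refit the cost and the complication-free regressions on the same resampled data and keep the pair of differences.
- Put ward and calendar-month terms in both models.
- Name the resampling unit and make it respect the ward clusters.
- State how the bootstrap is combined across the 200 imputed datasets.

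From the pairs, report incremental net benefit with a 95% interval, and the probability that PASC is cost-effective, over a stated range of values per complication-free admission. Base the conclusion of part d) on these. The threshold points and bed-day price quartiles can stay as deterministic sensitivity analyses.

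Cost: a short paragraph in part d) and some extra programming, because bootstrap and imputation have to be nested. No new data are needed. The interval will usually be wider than the cost interval alone, and the sponsor must commit to a value range in advance.

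### The QALY-equivalent figure in part d is a cost difference rescaled by a threshold, not a measure of effectiveness; part d also names two primary outcomes and gives patient costs no stated route into total costs

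*SAP*

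**What the plan says.** The SAP's introductory overview states for work package d that "the primary outcome is cost-effectiveness of the implementation across a-c", and adds: "Secondary outcomes are the patient costs attributed associated with their surgical treatment". The section for part d gives the hypothesis as "The main hypothesis is that the PASC is cost-effective for both patients and society" but names another primary outcome: "Primary outcome is costs associated with implementation of the PASC, where length of hospital stay is a major component for the overall treatment cost".

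The costing variables are listed under *Statistical power of the PASC trial on PASC-HEI*. Besides implementation costs, "the variables also include costs for the patients due to actions taken after using the PASC checklist"; the examples are general practitioner, dentist and diet. The patient data come from the trial data and from the PASC-HEI survey of a random sample (50 per cluster in each arm, 700 in all). The survey is compared between arms by a chi-squared or t-test, with a linear model where patient characteristics differ.

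The section *Statistical analysis plan of the PASC-Health Economic Impact data* then describes two calculations:

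- A regression for "mean differences of the total costs per admission and the probability of hospital admissions without complications", with the effect counted as 30-day complication-free admissions per 100.
- A conversion, to "express the estimated cost difference as a 'quality adjusted life year' (QALY", at a threshold of 43% to 93% of national income per head: "We will present QALY equivalent effectiveness of the PASC as the lower, mid-point and upper-bound of this range".

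**The concern.** A cost-effectiveness result sets a cost difference against a health effect. In the conversion, the item labelled as effectiveness is made from the cost difference itself. A saving with no health gain would appear as positive effectiveness. A real fall in complications bought at a small net cost would appear as negative effectiveness. Set beside the cost result as if it were a separate benefit, the figure would count the same saving twice.

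Two further points affect what part d can conclude. With two primary outcomes named, the headline result can be chosen after the data are seen. And a hypothesis about patients and society needs a cost measure that includes patient costs, but the SAP does not say whether or how they enter.

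**Working it through.** **1. What enters the QALY figure.** The SAP names a cost difference, for a bed-day equivalent, and a threshold. The EQ-5D-3L is collected in the same trial but its section is not linked to part d. The SAP prints no formula, so I take the natural reading, with a saving counted as positive:

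QALY equivalent per 100 admissions = 100 × S / (k × G)

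Here S is the saving per admission, G is national income per head, and k is 0.43, 0.68 or 0.93. The mid-point is (0.43 + 0.93)/2 = 0.68. The SAP gives neither S nor G, so S is expressed below as an assumed share of G, which then cancels.

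| Assumed S (share of G) | k = 0.43 | k = 0.68 | k = 0.93 |
|---|---|---|---|
| +1% | 2.33 | 1.47 | 1.08 |
| 0 | 0 | 0 | 0 |
| −2% (net cost) | −4.65 | −2.94 | −2.15 |

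For example, 100 × 0.01/0.43 = 2.33. The complication rate appears nowhere in the formula. The spread across the range is fixed at 0.93/0.43 = 2.16, and the lowest threshold gives the largest figure in absolute size.

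**2. What the figure cannot show.** The power section of part a plans for a fall from 15% to 10%, which is 5 more complication-free admissions per 100. At zero net cost the figure is still 0. If each avoided complication were worth 0.01 to 0.05 QALY (an assumption; the SAP gives no such weight), the true gain would be 5 × 0.01 = 0.05 to 5 × 0.05 = 0.25 QALY per 100 admissions, and all of it would be missed.

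**3. Primary outcome.** The overview names cost-effectiveness, which compares costs with effects. The part d section names implementation costs, which contain no effect. These are different quantities.

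**4. Patient costs.** The SAP lists them as variables and plans to compare the survey between arms. The regression uses total costs per admission without listing the components; the surrounding text speaks of implementation costs, hospital admission costs and bed-day costs. The survey covers at most 700 of the 5320 planned cases (700/5320 = 13%), so carrying its costs into a per-admission total needs a rule, and none is given.

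The choice could matter. With the assumed 1% saving and k = 0.43, assumed incremental patient costs of 0.5%, 1.0% and 1.5% of G give 100 × (0.01 − 0.005)/0.43 = +1.16, then 0, then −1.16. These amounts are illustrative.

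**The case against.** The strongest reply is that the conversion is an extra presentation. The cost-effectiveness analysis itself has a health outcome, complication-free admissions, reported alongside. The label says QALY equivalent, which signals a conversion. Complications can reach the figure indirectly, through length of stay and so through cost. The formula is inferred, because the SAP relies on the group's published evaluation of the WHO checklist, which is not at hand. The 2.16 factor only describes a range that the SAP openly commits to showing. All of this is fair, and it limits the point to the conversion and its label. It does not rescue the word effectiveness: a health effect that acts only through cost is already in the cost result.

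A reader might go further in three ways that the SAP does not support:

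- *Patient costs are excluded, or set to zero.* The overview makes them a secondary outcome and the part d section lists them among the variables. Total costs are undefined, which is not the same as excluding patient costs, so a bias in favour of PASC is possible but not established.
- *Control patients can have no such costs, so comparing arms is pointless.* The survey goes to both arms and its items are not shown. Control patients may also see a general practitioner or dentist before surgery, and the between-arm difference is what estimates the incremental cost.
- *Nothing about cost-effectiveness can be concluded.* A hospital-perspective cost per complication-free admission remains available from the planned regressions.

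**Conclusion.** The concern holds in this form. The planned QALY equivalent is a rescaled cost difference: its sign is that of the saving, it is 0 at zero net cost whatever happens to complications, and for one cost difference it varies by a factor of 2.16 with the threshold alone. It cannot show a health gain and should not be called effectiveness. This rests on reading the conversion as cost difference divided by threshold, which the SAP's wording supports but does not write out.

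Part d also needs one primary outcome in place of two, and a stated perspective with a matching definition of total costs. As written, the SAP does not support a conclusion for patients and society, although one for the hospital remains possible. The effect of patient costs on the result cannot be sized from the SAP. The changes should be made before the economic analysis; the trial's primary complication analysis does not depend on them.

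**What to change.** 1. Make the incremental cost per additional 30-day complication-free admission the single primary result of part d, built from the two differences the regression already estimates, and align the overview and the part d section on it.
2. Present the threshold conversion only as the health opportunity cost of the cost difference (or the QALY value of resources released). Drop the word effectiveness, and do not count the conversion beside the cost result as a separate benefit.
3. Define total costs per admission and the perspective. Then either add the incremental patient-paid cost estimated from the PASC-HEI survey, keeping the between-arm comparison, as a societal-perspective scenario, or limit the conclusion to the hospital perspective.

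The cost is SAP rewording and, if the societal option is chosen, one added scenario from data already planned. The downside is that no QALY gain can be claimed from the conversion, and the societal result may be less favourable to PASC.
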